### 14.1.3 Handling of unscheduled assessments

Generally, only the original scheduled assessments will be used for the analysis tables and unscheduled assessments will only be shown in listings. However, unscheduled assessments will be used for analysis tables in the following cases

- Use as baseline (see section 5.3.1)
- Worst-case determination over a period of time.
- Time to calculation e.g. Nasal mid-turbinate swab collected at unscheduled visits will be used to determine the time-to-BQL and time to undetectability.
- AUC calculation
- LOCF imputation of missing individual GSS items (see section 14.2.2)

### 14.1.4 Prior and Concomitant medication: Handling of missing/partial date

In case of missing or partial start or stop dates, no imputations will be performed, the therapy will be classified as prior or concomitant, as reported in the CRF.

### 14.1.5 Number of days between symptom onset and first dose of study drug: Handling of missing time part

Number of days between symptom onset and first dose of study drug is defined as the time between start of the symptom(s) (RSV disease characteristics) and first dose.

If needed time for start of the symptoms will be imputed with 00:00.

## 14.2 Efficacy

### 14.2.1 Viral load

#### 14.2.1.1 Area under the curve (AUC)

The area under the curve (from first study drug administration to time t) is the total viral load concentration over time. The total area is a plot of viral load (Y-axis) versus time (X-axis). The X-axis starts at timepoint t=0 (first study drug administration) and ends at last measurement (timepoint=t). The Y-axis represents the actual concentration at timepoint t. The AUC will mathematically correspond to the definite integral of the function (concentration curve). In

practice, the actual concentration is measured at certain discrete points in time and the trapezoidal rule is used to estimate AUC:

- $AUC(0) = 0$  at baseline  $t=0$ .
- $AUC(t) = AUC(t-1) + 0.5 * (Value(t-1)+Value(t)) * (time(t)-time(t-1))$  = cumulative AUC up to time  $t$ .

The actual times will be used to derive the AUC.

Rules on how to deal with missing values when deriving the AUC:

- If the baseline value is missing, then all AUCs will be set to missing.
- If single intermediate values (not the baseline nor the last value, and not more than 3 (in total, not consecutive)) are missing, then the missing value will be replaced by linear interpolation of the two adjacent values. Note: this is done automatically when applying the trapezoidal summation rule.
- If multiple ( $>1$ ) adjacent values are missing or more than 3 values are missing, then the AUC will also be set to missing.
- Unscheduled assessments will be considered for AUC calculation but will not be considered when defining the number of missing values.

#### 14.2.1.2 Time weighted average change from baseline to time $t$

- Time weighted average change from baseline to time  $t$  will be calculated as:

$$[AUC(t) - (\text{baseline value} * t)] / t.$$

For subjects who only have data up to time  $x (< t)$ , the time weighted average change from baseline to time  $t$  is defined as:  $[AUC(x) - \text{baseline value} * x] / x$ .

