# SCHEDULE OF ASSESSMENTS

Period	Screening a, b	Study Drug Treatment Period c									In-hospital Post-Treatment Period d	FU visit (Day 14±2) or Withdrawal visit e	EOS e (Day 28±2)			
		Hospitalized Dosing						Hospitalized or Ambulatory Dosing								
		Day 1			Day 2			Day 3								
Visit	-24h to randomization	-3h to dose	Dose	2h (±0.5h)	5h (±1h)	-2h to dose	Dose	2h (±0.5h)	5h (±1h)	-2h to dose	Dose	2h (±0.5h)	Morning and evening			
Informed consent	X															
Inclusion/exclusion criteria	X															
RSV diagnosis f	X															
Demographics and medical history	X															
Hospitalization information/Clinical response information g																→
Study drug administration h			X				X				X					
Nasal mid-turbinate swab i		X			X	X			X	X		X	X j	X		
Physical examination k	X	X			X	X			X	X		X	X	X	X	X
Body weight	X														X	X
Body height	X														X	X
Body temperature	X	X			X	X			X	X		X	X	X	X	X
General appearance	X	X			X	X			X	X		X	X	X	X	X
Lung auscultation n	X	X		X	X	X		X	X	X		X	X	X	X	X
Heart rate	X	X		X	X	X		X	X	X		X	X	X	X	X
SpO 2 l	X	X		X	X	X		X	X	X		X	X	X	X	X
Feeding m	X	X			X	X			X	X		X	X	X	X	X
(Respiratory muscle) retractions	X	X		X	X	X		X	X	X		X	X	X	X	X
Respiratory rate	X	X		X	X	X		X	X	X		X	X	X	X	X
Randomization b		X														
Daytime coughing	X	X		X	X	X		X	X	X		X	X	X	X	X
(Sleep disturbance from) night-time coughing o	X o	X o				X o				X o			X o	X o	X o	X
Parent/caregiver assessment p																→
Pharmacokinetics (single sample)																← → q
Pharmacokinetics (more extensive sampling)						X r										← → r ← → r
Clinical laboratory (hematology and clinical biochemistry)	X s, t														X u	
Immunogenicity	X s														X u	
Previous and concomitant medication																→
Adverse events v																→

h = hour; FU = Follow-up; EOS = End of Study.

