### **3.4.1.2. STUDY DRUG TREATMENT AND IN-HOSPITAL POST-TREATMENT PERIOD**

During the study drug treatment period, assessments should be performed as detailed in the [Schedule of Assessments](#).

If the Day 1, pre-dose assessments will be performed within 3 hours after the screening assessments have been performed, the assessments already done at screening do not need to be repeated and only the additional assessments to be performed on Day 1, pre-dose will need to be performed.

Subjects will receive once-daily administration of study drug on 3 consecutive days. The first dose of study drug is to be administered as soon as possible and within 3 hours after randomization. For all subjects, the exact date and start and end time (and number of interruptions, if any) of the study drug nebulizations will be collected in the eCRF.

Provided that the clinical response criteria have been met, discharge from the hospital can take place per protocol at the Investigator's discretion from dosing Day 2 onwards after all required assessments of the 5 hours ( $\pm 1$  hour) post-dose time point have been completed. Subjects discharged after the second dose must return to the hospital for the third study drug administration (to be administered  $48 \pm 4$  hours after the first dose by the appropriately trained study personnel), and be monitored for a 2-hour pre- and post-dose period.

Subjects who are still hospitalized during the post-treatment period will be followed up twice daily (in the morning and the evening) until the subject is discharged from hospital.

Hospitalization information will be collected during the study drug treatment period and the in-hospital post-treatment period, including occurrence of ICU transfer, apnea episodes, initiation and type of ventilation and hospital/ICU discharge information. Assessment of Clinical Response will be done with collection of date and time of adequate oral feeding to enable discharge as well as adequate stable oxygen saturation on room air of >92% over a period of at least 4 hours. For subjects in the in-hospital post-treatment period, the nasal swab should be collected only on the day of hospital discharge.

All assessments will be performed as specified in the [Schedule of Assessments](#).

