### 7.2.2.2 Viral Load

In this study, viral titers are measured using the plaque assay for the primary endpoint and by RT-qPCR for the secondary endpoint(s). As secondary endpoint, the time to BQL using RT-qPCR will be summarized using KM estimates. No p-values will be provided.

The time to undetectability (hours) defined as the time from the first study drug administration to first occurrence of viral titer below the lower limit of quantification (LLOQ) and target not detected, provided the next measured value is below the quantification limit and undetected as well, will be summarized using KM estimates, based on the plaque assay and RT-qPCR. The time to event for subjects with missing data and/or who did not reach undetectability during the trial will be censored at the last nonmissing viral load assessment .

In addition, the number and percentage of subjects that have viral titers BQL (for both virus and RNA) and with undetectable viral load will be tabulated over time.

Viral load measured by plaque forming unit assay (log10 PFU/mL) and by RT-qPCR (log10 viral copies/mL) will be summarized as continuous variables:

- Viral load (actual values and absolute change from baseline) in nasal swab specimens (RT-qPCR and plaque assay) will be presented using descriptive statistics (see section 5.4.1) over time. Viral load will also be presented graphically by plots describing the mean over time (+SE).

For the summary statistics, samples that are below the lower limit of quantification (LLOQ) (i.e. BQL) will be assigned a value of half the LLOQ level.

- Time weighted average change from baseline up to Day 3 and Day 14 (both virus and RNA) (see section 14.3.1 for calculation method).

Viral load analysis will be performed on mITT and RSV infected population

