**Table 14.2.3.5: Viral load - Time weighted average change from baseline .**

Descriptive statistics of Time weighted average change from baseline to Day 3 and to Day 14 per assay.  
Part 1 : Modified intent-to-treat population.  
Part 2 : RSV infected population

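### Without a Day 14 swab, the SAP reports a shorter average (about 2 days, or up to discharge) as the Day 14 time-weighted viral load change

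*SAP*

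**What the plan says.** SAP 7.2.2.2 lists a time-weighted change in viral load to Day 3 and to Day 14, for plaque and RT-qPCR, within the secondary viral load endpoint. The output is Table 14.2.3.5: "Descriptive statistics of Time weighted average change from baseline to Day 3 and to Day 14 per assay".

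SAP 14.2.1.1 builds the AUC by the trapezoidal rule from first dose to the last measurement: "The actual times will be used to derive the AUC". The AUC is set to missing if baseline is missing, if more than one adjacent value is missing, or if more than three values are missing in total. Extra swabs enter the area but not the count: "Unscheduled assessments will be considered for AUC calculation but will not be considered when defining the number of missing values".

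SAP 14.2.1.2 divides [AUC(t) - baseline × t] by t. The exception begins "For subjects who only have data up to time" x, earlier than t, and gives [AUC(x) - baseline × x]/x as the value to t. It sets no lower limit on x, no flag and no sensitivity analysis.

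The Protocol's Schedule of Assessments has six swabs from Day 1 pre-dose to Day 3, 2 h post-dose, and then one at the Day 14 (± 2) follow-up or Withdrawal visit. Between them, Protocol 3.4.1.2 plans one swab at most: "For subjects in the in-hospital post-treatment period, the nasal swab should be collected only on the day of hospital discharge". Infants already discharged by Day 3 have none, unless they are re-hospitalized or seen again for a respiratory condition.

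**The concern.** A time-weighted change grows with the length of the averaging period for as long as virus is below baseline and still falling. An average over 2 days and one over 13 days are then different quantities, even in the same infant. The substitution rule gives both the same label and puts them in the same mean. Arms that differ in Day 14 attendance would differ in this summary even with identical viral courses.

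The sparse schedule adds a second, milder problem for infants who do attend on Day 14. With no swab after Day 3, a single straight line stands for most of the period. With a discharge swab, the value depends on when that swab was taken. The table belongs to a named secondary endpoint in a study meant to support dose selection, so a reader may compare the arms on it.

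**Working it through.** The plan states no figure for this quantity, so there is none to reproduce. The documents give neither a viral curve nor the LLOQ. The log10 sizes below therefore rest on assumed curves; the timing does not.

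**1. Is an infant with only Day 14 missing set to missing?** No. Baseline is present, one value is absent, and that value is the last one, so the interpolation rule for single intermediate values does not apply either. SAP 14.2.1.2 then supplies the value at x.

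**2. Timing.** First dose is Day 1 and there is no Day 0 (SAP 14.1.2), so Day 14 is 13 × 24 = 312 h. The third dose is at 48 h and the last Day 3 swab 2 h after it, nominally at 50 h.
- Share of the period with no swab, for infants with none between Day 3 and Day 14: (312 - 50)/312 = 84.0%.
- Follow-up visit on Day 12: (264 - 50)/264 = 81.1%. On Day 16: (360 - 50)/360 = 86.1%.
- With Day 14 missing and no later swab, x is about 2.1 days.

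**3. Size.** Assume V(t) = max(F, V0 - s·t), with swabs at 0, 5.3, 24, 29.3, 48 and 50.5 h (allowing for nebulization time). The floor is reached at T = (V0 - F)/s days.
- True change to Day 14 = -(V0 - F) × (1 - T/26). First RNA curve: T = 4.5/0.8 = 5.625, giving -4.5 × (1 - 5.625/26) = -3.53.
- If the fall is still linear at x, the SAP value is -s·x/2. First RNA curve, x = 50.5/24 = 2.104 d: -0.8 × 2.104/2 = -0.84. With a day-5 discharge swab: -0.8 × 5/2 = -2.00.
- If the floor is reached before x, the value is -(V0 - F) × (1 - T/(2x)). Plaque with T = 1: -2.6 × (1 - 1/4.208) = -1.98.

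| Assumed curve (log10) | True, to Day 14 | SAP, Day 14 swab present, no discharge swab | SAP, Day 14 swab missing, none after Day 3 |
|---|---|---|---|
| RNA: 7, falling 0.8/day to 2.5 | -3.53 | -2.73 | -0.84 |
| RNA: 6, falling 0.6/day to 2.5 | -2.71 | -2.10 | -0.63 |
| Plaque: 4, falling 0.7/day to 1.4 | -2.23 | -1.83 | -0.74 |
| Plaque: 4, reaching 1.4 at 1 day | -2.50 | -2.50 | -1.98 |

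**4. Effect on an arm mean.** Suppose 10 percentage points more infants in one arm lack a Day 14 swab and have none after Day 3 (an assumption). With identical viral courses, the arm mean shifts by 0.10 × (2.73 - 0.84) = 0.19 on the first curve, 0.10 × (2.10 - 0.63) = 0.15 on the second, 0.10 × (1.83 - 0.74) = 0.11 on the third and 0.10 × (2.50 - 1.98) = 0.05 on the fourth.

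**5. Discharge-swab date, Day 14 swab present.** On the first curve, a discharge swab at elapsed day 3, 5, 6, 8 or 10 gives -2.93, -3.38, -3.49, -3.27 or -3.05, against -2.73 with none. The value moves towards the truth and then away from it.

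**The case against.** The strongest reply is that little depends on this number. It is summarised descriptively without a test, and Table 14.2.3.5 does not carry the mark that SAP Section 16 uses for topline outputs. It enters neither the primary log-rank test nor the Global Severity Score model. The Day 3 average, viral load by visit and the percentages below quantification or undetectable are all planned, and individual viral loads are listed. All of this stands and limits the weight of the point. It does not make a 2-day average a Day 14 value.

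The second reply is that the sizes are assumed. That also stands. The sample-size section assumes a median plaque time-to-BQL of 0.5 day on drug and 1 day on placebo. An infant who is below quantification by about 1 day and stays there has a flat curve afterwards. The discharge date then has no effect, and the substitution costs about 0.5 log10 (2.50 - 1.98 = 0.52).

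Two stronger readings are tempting. A reader might infer that every Day 14 value rests on one line over 84% of the period and falls back to 2 days when Day 14 is missed. The schedule does not support that: infants still in hospital after treatment have a discharge swab, and withdrawn infants have one at the Withdrawal visit. The documents do not give the share in each group. A reader might also infer that shorter stay always makes decline look smaller, so that the bias runs against the better arm. Step 5 of the working shows the effect is not monotone: moving discharge from day 10 to day 6 makes the decline look larger.

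**Conclusion.** The point holds for the substitution rule. As written, the SAP labels an average over about 2 days, or up to the discharge swab, as an average to Day 14 and pools it with values that do reach Day 14. That follows from the text alone. Whether it matters numerically depends on virus still falling after Day 3. If it is, the assumed RNA curves give a shortfall of 3.53 - 0.84 = 2.69 or 2.71 - 0.63 = 2.08 log10 for an affected infant, and 3.53 - 2.00 = 1.53 on the first curve with a day-5 discharge swab. For plaque under the planning assumption it is about 0.5.

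The long unsampled interval and the dependence on discharge date are limits of the schedule. They call for cautious reading of the Day 14 value. The documents do not fix a direction of bias between arms, which would need the discharge distribution. The primary conclusion is untouched.

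One ambiguity remains. When several final swabs are missing, the SAP does not say whether the set-to-missing rule in 14.2.1.1 or the substitution in 14.2.1.2 applies.

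**What to change.** In SAP 14.2.1.2, state that the substitution does not apply to the Day 14 time-weighted change. Set that value to missing when no swab falls within Day 14 ± 2 days, and show the number excluded per arm in Table 14.2.3.5. This also settles, for Day 14, which missing-data rule governs.

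Keep the Day 3 time-weighted change as the main AUC summary. It rests on closely spaced swabs, although infants who stop study drug early may lack some of them. Read the Day 14 value beside the planned change from baseline and the percentages below quantification or undetectable at that visit.

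A Day 14 average from the common scheduled swabs alone could be an optional sensitivity analysis. It should not replace the main calculation: on the first assumed curve it would give every infant -2.73 against a true -3.53 and would discard real discharge data.

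The cost is a wording change and a simpler derivation, with no new data. Infants without a Day 14 swab leave this one summary, which becomes a complete-case summary; the exclusion counts per arm let the reader judge that.

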#### 14.2.2 Global Severity Score (GSS)

GSS will be calculated by summing the scores of 7 individual items (see below). Maximum score is 20 with higher score indicating a more severe disease.

For the computation of the baseline GSS, the baseline value of each individual item is first identified (some may be from Day 1 pre-dose and others from screening). The individual item baseline values are then summed to obtain the baseline GSS.

Apnea, hospital stay, oxygen supplementation, and ventilation will be considered respectively to have occurred at the considered visit and time point if they are reported over a period that covers at least partly the time interval defined for this visit using following definitions for time intervals:

- for baseline : from hospital admission to first study drug administration,
- for post-baseline visits and timepoints during treatment as:
  - starting from the minimum between:
    - the end of the previous interval,
    - the earliest date and time a GSS component was assessed at the considered visit and timepoint, and
    - 1 minute before the latest date and time a GSS component was assessed at the considered visit and timepoint

- - ending at the latest date and time a GSS component was assessed at the considered visit and timepoint.
- for all ‘Post-Treatment Day n’ visits:
  - the “MORNING” timepoint will be assigned to time interval 00:00 – 11:59 of the date of the considered visit and timepoint
  - the “EVENING” timepoint will be assigned to time interval 12:00 – 23:59 of the date of the considered visit and t timepoint
- The “Follow-UP” visit and unscheduled post-treatment visits will be assigned to time interval 00:00 – 23:59 of the date of the considered visit and timepoint. This implies that there will be a gap between the follow-Up visit and the previous timepoint, and that every hospitalization / apnea / ventilation / oxygen supplementation recorded that would be entirely within that gap will not be taken into account into GSS score computed at any timepoint.

This implies that a recorded item (hospitalization / apnea / ventilation / oxygen supplementation) may contribute to more than one time interval for the GSS calculation.

Item	Number of Points	Description
Feeding	0	Adequate oral feeding
	1	No adequate oral feeding, occasional breaks during feeding
	2	No adequate oral feeding, frequent breaks during feeding
	3	No adequate oral feeding, unable to feed, or on feeding support
Medical interventions	0	Not hospitalized
	1	Hospitalization without O 2 supplementation
	2	Conventional oxygen supplementation
	3	Non-invasive respiratory support or invasive ventilation
Respiratory distress	0	RDAI = 0
	1	RDAI ≥ 1 to < 6
	2	RDAI ≥ 6 to ≤ 11
	3	RDAI > 11
Respiratory rate	0	<2 months: ≤50 bpm; 2-<6 months: ≤45 bpm; 6-<12 months: ≤40 bpm; 12-24 months: ≤35 bpm
	1	<2 months: >50 to ≤60 bpm; 2-<6 months: >45 to ≤55 bpm; 6-<12 months: >40 to ≤50 bpm; 12-24 months: >35 to ≤45 bpm
	2	<2 months: >60 to ≤70 bpm; 2-<6 months: >55 ≤ 60; 6-<12 months: >50 to ≤55 bpm; 12-24 months: >45 to ≤50 bpm
	3	<2 months: >70 bpm; 2-<6 months: >60 bpm; 6-<12 months: >55 bpm; 12-24 months: >50 bpm
Apnea	0	No apnea episode
	3	Apnea episode
General appearance a	0	Active, playing/ content/ interactive and happy
	1	Less active/ mildly irritable/ less interactive or responsive
	2	Less active/ moderately irritable/ less interactive or responsive
	3	Not active/ Severely irritable/ Not interactive or not responsive

Note: In case worst item is less active and/or less interactive: if both are present: 2 points; if only one of both is present and the highest: 1 point

Body Temperature	0	<37,0°C: (measured axillary); <37,5°C (measured by other method)
	1	≥37,0°C but <38°C (measured axillary); ≥37,5°C but <38,5°C (measured by other method)
	2	≥38°C (measured axillary); ≥38,5°C (measured by other method)

a Assessed through activity, irritation and interest in environment (worst of the three items will be used for attributing the points)

Following imputation will be done for missing data :

- For General appearance, scoring will be done only on completed items and only the worst item is used for scoring.
- If more than two individual items (i.e., feeding, medical intervention, RDAI, respiratory rate, general appearance and body temperature) are missing at a given timepoint GSS will be set to missing for this timepoint
- If maximum 2 individual items are missing at a timepoint, missing items will be imputed using LOCF approach and the GSS will be calculated after imputation of the individual item(s).
- 

Imputed items will be flagged in the listings.

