**Figure 4: Overview of study flow**

Subjects will be screened as soon as possible after arrival to the hospital/emergency unit. After completion of the screening assessments and confirmation of subject's eligibility, randomization should follow as soon as possible but not more than 24 hours after arrival. Study drug administration should start as soon as possible after randomization with a maximum time interval of 3 hours following randomization. Subsequent doses of study drug will be administered at 24-hour intervals ( $\pm 4$  hours) relative to the first dose. No premedication is required or recommended per protocol, but an inhaled  $\beta 2$ -agonist may be administered at the discretion of the treating Investigator.

On the first 2 dosing days, inpatient hospital stay is required. Provided that the clinical response criteria have been met (which are based on adequate oral feeding and oxygen saturation), discharge from the hospital can take place per protocol at the Investigator's discretion from dosing Day 2 onwards after all required assessments of the 5 hours ( $\pm 1$  hour) post-dose time point have been completed. Subjects discharged after the second dose must return to the hospital for the third study drug administration (to be administered  $48 \pm 4$  hours after the first dose by the appropriately trained study personnel), and be monitored for a 2-hour pre-dose and post-dose period. Subjects who are not discharged

from the hospital after completion or premature discontinuation of study drug enter an in-hospital post-treatment period with assessments in the morning and evening. A Follow-Up (FU) visit is scheduled on Day 14 ( $\pm$  2 days), and an End of Study (EOS) visit on Day 28 ( $\pm$  2 days). For subjects prematurely withdrawn from the study, a Withdrawal visit is to be performed on the day of withdrawal.

The primary endpoint in this study is the evaluation of viral load in samples obtained via nasal mid-turbinate swabs. In particular, the time needed for the viral load (as assessed by plaque assay) to drop below the quantification limit (BQL) is calculated (time-to-BQL).

Secondary endpoints include:

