### 5.3 Key Definitions

#### 5.3.1 Definition of baseline

Baseline is defined as the last non-missing assessment before first administration of study drug.

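### Brief apnea or oxygen episodes falling between the start of dosing (Day 1) or the pre-dose check (Day 2) and the 2 h assessment enter no Global Severity Score, because the 2 h timepoint closes an interval but has no computable score

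*SAP*

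**What the plan says.** SAP 14.2.2 scores four things from event records rather than from a bedside assessment: apnea, hospital stay, oxygen and ventilation. Each counts at a timepoint "if they are reported over a period that covers at least partly the time interval defined for this visit".

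- **Baseline interval:** "for baseline : from hospital admission to first study drug administration".
- **On-treatment intervals:** each starts at the earliest of three times, normally "the end of the previous interval", and finishes "ending at the latest date and time a GSS component was assessed at the considered visit and timepoint".
- **Missing scores:** when more than two of six named items (feeding, medical intervention, RDAI, respiratory rate, general appearance, body temperature) "are missing at a given timepoint GSS will be set to missing for this timepoint". With one or two missing, the last observation is carried forward.
- **Acknowledged gap:** the section mentions one gap only, before the Follow-up visit.

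The Schedule of Assessments has lung auscultation, retractions and respiratory rate at 2 h after dosing on Days 1 and 2. It does not have feeding, general appearance or body temperature there. All three schedule versions in SAP Appendix A agree. On Day 3 all of these are scheduled at 2 h, so Day 3 is unaffected.

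SAP 7.2.1 makes change from baseline in GSS to Day 2, 5 h the key secondary endpoint. It is tested in a mixed model with baseline as a fixed effect, using data through Day 3.

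**The concern.** The on-treatment intervals are built to be contiguous, so a reader would expect every event from first dose through Day 3 to reach some GSS value. Two rules interact to prevent this. The interval rule gives the 2 h timepoint its own slice of time. The missing-data rule then withholds a score from that slice. The next score, at 5 h, starts counting only after the 2 h assessment.

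Take an infant with one apnea half an hour after the second inhalation on Day 2 and none otherwise. The Day 2 pre-dose interval has closed, the 2 h score does not exist, and the 5 h interval has not opened. The apnea item is 0 at every scored timepoint. SAP 7.2.1 also summarizes GSS subitems only where the GSS is not missing, so the event does not appear in the GSS subitem tables either.

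The slice that drops out is the one around and just after inhalation. Protocol 1.3.3 names airway hyperresponsiveness after inhalation as a risk to be watched closely. GSS change is also the only clinical endpoint for which the SAP plans a formal test between arms; time to clinical response has Kaplan-Meier summaries only.

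**Working it through.** The documents state no window length, so there is no plan figure to reproduce. The check is interval arithmetic on the SAP 14.2.2 rules and the Schedule of Assessments.

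**1. Is the 2 h GSS computable on Days 1 and 2?** Available: RDAI, respiratory rate, and medical intervention (from records). Not scheduled: feeding, general appearance, body temperature. Missing = 3, allowed = 2, and 3 > 2, so the GSS is missing by design.

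**2. Length of the Day 2, 5 h window.** Inputs: 2 h ± 0.5 h and 5 h ± 1 h, both measured from the end of the second nebulization.
- Nominal: 5 − 2 = 3 h
- Shortest: (5 − 1) − (2 + 0.5) = 1.5 h
- Longest: (5 + 1) − (2 − 0.5) = 4.5 h

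**3. Length of the slices that reach no score.** Nebulization time: Protocol 3.3.7.1 gives about 4 min per 0.5 mL, or 8 min per mL. Table 1 total volumes run from 0.20 + 0.40 = 0.60 mL to 0.75 + 1.5 = 2.25 mL, which gives 4.8 to 18 min (0.08 to 0.30 h). Protocol 3.3.7.2 allows up to 4 h for both nebulizations.
- Day 1, first dose to the 2 h assessment: 0.08 + 2 = 2.08 h to 0.30 + 2 = 2.30 h; at the extreme 4 + 2.5 = 6.5 h.
- Day 2, last pre-dose assessment (0 to 2 h before dosing) to the 2 h assessment: 0 + 0.08 + 1.5 = 1.58 h to 2 + 0.30 + 2.5 = 4.8 h; at the extreme 2 + 4 + 2.5 = 8.5 h.

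**4. Which events are lost.** Because partial overlap is enough to count, an event is lost only if it both
- starts after the preceding interval closes (first dose on Day 1; last pre-dose assessment on Day 2), and
- ends before the 2 h assessment.

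**5. Effect on the Day 2, 5 h contrast.** Apnea scores 3 or 0. If one arm has an excess proportion p of infants with an uncounted apnea on Day 2, the mean shift is 3p:

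| Assumed p | Shift (points) | Share of the planned 2 points |
|---|---|---|
| 1% | 0.03 | 1.5% |
| 5% | 0.15 | 7.5% |
| 10% | 0.30 | 15% |

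For a brief oxygen episode the medical-intervention item moves from 1 to 2, so the shift is p: 0.01 to 0.10 points over the same range. The documents give no rate; these values of p are assumptions.

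**6. Baseline look-back, for comparison.** The Protocol says "randomization should follow as soon as possible but not more than 24 hours after arrival" and "Study drug administration should start as soon as possible after randomization with a maximum time interval of 3 hours following randomization", so the maximum is 24 + 3 = 27 h from arrival. The rule itself starts at admission, so 27 h is an upper bound.

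**7. Window after the proposed change.** Day 2, 5 h would run from the end of the pre-dose interval: 0 + 0.08 + 5 = 5.08 h to 2 + 0.30 + 5 = 7.30 h at nominal 5 h timing, with extremes of 0 + 0.08 + 4 = 4.08 h and 2 + 4 + 6 = 12 h.

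**The case against.** **The gap rests on one reading.** The SAP never says whether a timepoint without a computable GSS closes an interval. If it does not, the 5 h interval absorbs these events. That is fair, but the literal text points the other way, and two programmers could derive different key secondary values. Also, if one of the three unscheduled items happened to be collected at 2 h, two would remain missing and the score would be filled by carry-forward. So missing by design is correct; always missing is not.

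**A reader might infer that any event ending within 2 h of inhalation is lost.** It is not. Oxygen already running at first dose counts at baseline, and oxygen running at the Day 2 pre-dose assessment counts there. Anything continuing past the 2 h assessment counts at 5 h. Ventilation hardly fits the gap, since starting respiratory support ends study drug and moves the infant to post-treatment follow-up. What remains is isolated apnea and very short oxygen episodes.

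**A reader might infer that post-inhalation harm is hidden.** The documents do not support that. Apnea must be reported as an adverse event, and initiating respiratory support triggers SAE reporting (Protocol 3.4.8.1). SAP 7.3 tabulates apnea and ventilation incidence and oxygen duration. The IDMC sees unblinded safety data. The defect is confined to the GSS.

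**A reader might infer that a baseline look-back of up to 27 h against about 3 h biases the treatment comparison, or breaks the general definition in SAP 5.3.1** ("Baseline is defined as the last non-missing assessment before first administration of study drug"). Neither follows. The rule is the same in every randomized, blinded arm and baseline is in the model, so a shift common to all arms does not produce a difference between them. SAP 5.3.1 concerns assessments, while 14.2.2 gives a specific rule for event records, and SAP 14.2.6 defines baseline oxygen in the same since-admission way. Scoring apnea by status at the last pre-dose check would make a momentary event almost unscorable.

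**Conclusion.** The point holds in a limited form. On the literal text, brief apnea or oxygen episodes lying wholly within the 2 h intervals on Days 1 and 2 reach no GSS value, and the SAP does not acknowledge this. For the key secondary contrast only the Day 2 gap matters directly. The Day 1 loss affects the Day 1, 5 h score, which enters the model but is not the tested contrast.

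The size is probably small: 0.03 to 0.30 points for an assumed 1% to 10% excess of uncounted apneas in one arm on Day 2, against 2 planned points. Bias between arms requires such events to be unequal across arms, and the documents give no rate. The better reason to act is that the derivation of the key secondary endpoint should have one reading and should not omit the period around inhalation by accident.

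The since-admission baseline rule can stay. Because it looks back up to about 27 h, a within-arm fall from baseline in the apnea, oxygen and ventilation items should not be read as improvement.

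**What to change.** In SAP 14.2.2, state that only timepoints at which all GSS items are scheduled open and close an interval. The Day 1, 5 h interval then runs from first dose, and the Day 2, 5 h interval runs from the end of the Day 2 pre-dose interval. RDAI and respiratory rate at 2 h are still summarized under SAP 7.3 as planned. At the same time, correct the cross-reference in SAP 7.2.1, which sends the reader to 14.3.2 (laboratory evaluations) for the GSS computation.

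Cost: SAP wording and one derivation change before unblinding, with no new data. The Day 2, 5 h window lengthens from about 3 h to about 5 to 7 h, so the score reflects a longer recent period. Leave the baseline rule unchanged and add one sentence on its longer look-back where within-arm changes are presented.
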